6.2 Unit/department evaluation

24. Type of hospital (< 500 beds/500-1000 beds/ > 1000 beds)
25. Type of ICU (Medical/Surgical/Mixed/Specialised)
26. Number of ICU beds open for admission
27. Does your ICU have a general guideline/protocol for identifying delirium?
28. Does your ICU have a general guideline/protocol for interventions of delirium?
29. When do you intervene for delirium?
30. Are patient restrained in your ICU (never, sometimes, often)?
31. Average nurse to patient ratio during the day, evenings and nights.

7. Statistical Methods

7.1 Sample size estimation

In a case control study with a simple random sampling, and an estimated treatment prevalence of delirious patients treated with haloperidol in the ICU of 13% (preliminary data at Dept. of Intensive Care 4131, Rigshospitalet, Copenhagen from May 2014), inclusion of at least **1000** patients is required to yield a 95% confidence interval of a rate of haloperidol use of 11%-15%. With expected mortality rate of 30% 1000 patients will yield a 95% confidence interval of 23% - 38% for 90-day mortality. Fifty ICUs are estimated to include this sample of patients within 14 days ¹⁵.

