3.1 Type of study

A multicentre 14-day inception cohort study investigating the pharmacological intervention practices of delirium in acutely ill ICU patients (estimated 50 ICUs in 8 countries). The 14-day study period can be selected by sites from Marts 1st to May 30th 2016.

4. Method

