4.1 Number of subjects

We expect to include 1000 acutely ill patients admitted to the participating ICUs.

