7.3 Statistical plan

The number of patients receiving haloperidol (totally and regularly, as needed and mixed dosing) will be presented as frequencies (% with 95% confidence intervals). Numeric data will be given as medians (interquartile range [IQR]). We will compare differences in baseline characteristics using non-parametric tests between patients who receive haloperidol and patients who do not receive haloperidol. To assess risk factors for the use of haloperidol, we will do multivariate analyses including patient characteristics (age, dialysis, shock and mechanical ventilation and delirium in the first 24 h of admission) and ICU characteristic (university hospital, guidelines for identifying and/or treating delirium and average staff-patient ratio). To assess if haloperidol is an independent predictor of 90-day mortality, we will do multivariate analysis including patient characteristics (age, dialysis, shock and mechanical ventilation and delirium in the first 24 h of admission) and time. We will do exploratory analyses on the interaction between delirium and use of haloperidol and the patient-relevant outcomes measure (mortality, days alive without mechanical ventilation and days alive and out for hospital). All statistical tests will be 2-tailed and $p < .05$ considered statistically significant.

8. Data Handling

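### Section 7.1 derives the 11%-15% interval from a case-control study with simple random sampling, but the study is a cohort clustered in about 50 ICUs; no allowance is made for clustering

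*Protocol*

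**What the plan says.** Protocol section 7.1 sets the sample size by precision. It opens with "In a case control study with a simple random sampling", takes 13% as the rate of haloperidol use from preliminary data in one department, and says that at least 1000 patients "is required to yield a 95% confidence interval of a rate of haloperidol use of 11%-15" per cent. The ICUs enter the paragraph only as the means of reaching that number: "Fifty ICUs are estimated to include this sample of patients within 14 days".

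The design is described differently elsewhere in the protocol. Section 3.1 calls it a multicentre inception cohort ("estimated 50 ICUs in 8 countries"). Sections 5.1.1 and 7.2 take every acute adult admission to a participating ICU in its 14-day window, subject to the exclusions in 5.1.2. Section 4.1 repeats the number: "We expect to include 1000 acutely ill patients admitted to the participating ICUs".

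Section 7.3 plans percentages with 95% confidence intervals and a multivariable analysis of risk factors for haloperidol use. Besides patient factors, that analysis includes "ICU characteristic (university hospital, guidelines for identifying and/or treating delirium and average staff-patient ratio". The section does not name a type of model, a method for the intervals or any handling of ICU, and it does not say that patients will be treated as independent.

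**The concern.** A case-control study selects patients by outcome status, and a simple random sample draws patients independently from one population. This study does neither: it enumerates whole ICUs. Patients in one ICU share prescribers, guidelines and staffing, so their outcomes are likely to be correlated, and a binomial variance then understates the uncertainty.

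The protocol itself gives reasons to expect such correlation:

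- Section 7.3 treats guidelines, type of hospital and staffing as possible predictors of haloperidol use.
- Section 6.2 asks each unit about its delirium guidelines and when it intervenes.
- Section 6.1 lets each site record only the delirium score that it uses in practice. Delirium is part of the primary outcome (4.3.1), so ascertainment also differs by ICU.
- The 13% comes from one ICU and carries no information on the spread between ICUs.

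At stake is the expected precision of the primary outcome, which is the only justification given for 1000 patients.

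**Working it through.** **Inputs from the protocol.** Rate p = 0.13 and N = 1000 (7.1, 4.1); 50 ICUs (7.1, 3.1), so m = 1000/50 = 20 patients per ICU. As in 7.1, all 1000 patients are taken as the denominator.

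**Assumed inputs.** The protocol gives no ICC, so a range is shown. ICU sizes are taken as equal unless stated.

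**Step 1: reproduce the stated interval.** Under independence, p ± 1.96 × √(p(1−p)/N) = 0.13 ± 1.96 × √(0.1131/1000) = 0.13 ± 0.0208, or 10.9%-15.1%. The Wilson interval is 11.1%-15.2% and the exact interval 11.0%-15.2%. The stated 11%-15% is therefore the independence result.

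**Step 2: add the design effect.** DE = 1 + (m − 1) × ICC = 1 + 19 × ICC. The half-width becomes 1.96 × √(0.1131/1000 × DE). The effective sample size is 1000/DE. The last column is the true coverage of a nominal 95% interval that ignores clustering, 2Φ(1.96/√DE) − 1.

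| Assumed ICC | DE | Half-width (points) | Expected 95% CI | Effective N | Coverage if clustering is ignored |
|---|---|---|---|---|---|
| 0 | 1.00 | 2.1 | 10.9%-15.1% | 1000 | 95% |
| 0.01 | 1.19 | 2.3 | 10.7%-15.3% | 840 | 93% |
| 0.02 | 1.38 | 2.4 | 10.6%-15.4% | 725 | 90% |
| 0.05 | 1.95 | 2.9 | 10.1%-15.9% | 513 | 84% |
| 0.10 | 2.90 | 3.5 | 9.5%-16.5% | 345 | 75% |

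A beta-binomial simulation (50 ICUs of 20 patients, 20,000 runs) gave coverage of 93.1%, 84.1% and 75.1% at ICC 0.01, 0.05 and 0.10, in agreement with the formula.

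**Step 3: find where the stated interval fails.** It still rounds to 11%-15% while the half-width is at most 2.5 points. That allows DE = (0.025/1.96)² × 1000/0.1131 = 1.44, so ICC = 0.44/19 ≈ 0.023. At that ICC the between-ICU standard deviation of the haloperidol rate is √(0.023 × 0.1131) ≈ 0.051, about 5 percentage points around 13%.

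**Step 4: unequal ICU sizes.** With an assumed coefficient of variation of ICU size of 0.5, DE = 1 + ((1 + 0.5²) × 20 − 1) × ICC. At ICC 0.05 this is 1 + 24 × 0.05 = 2.20, and the interval is 9.9%-16.1%.

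**Step 5: what would follow in 7.3 if ICU were ignored.** For a yes/no ICU-level covariate with no effect, tested without adjustment in 25 against 25 ICUs, the true type I error of a nominal 5% test is 2(1 − Φ(1.96/√DE)). This gives 7% at ICC 0.01, 16% at 0.05 and 25% at 0.10; the simulation gave 7.2%, 15.8% and 25.0%.

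**The case against.** A reader might infer that the 11%-15% interval certainly will not be achieved. The documents do not support that. The outcome depends on an ICC that the protocol does not give, and up to about 0.023 with equal ICU sizes the interval still rounds to the stated one. What the protocol does show is that the figure was derived for a design the study does not have.

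A reader might also infer that the planned models assume independence and that their tests are therefore anti-conservative. Section 7.3 does not say so. The simple-random-sampling wording belongs to 7.1 alone. A random effect, robust standard errors or a particular interval method is commonly left to a statistical analysis plan, and none is at hand here. The type I error figures also come from a simple unadjusted comparison. The protocol plans a model with several patient and ICU factors together, and the correlation left after those factors may be smaller than the raw ICC. The 90-day mortality model lists no ICU-level covariates, so these figures do not apply to it. All of this stands, and it makes the 7.3 issue a conditional risk.

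Finally, the primary outcome is descriptive, with no test or decision threshold attached, and a half-width of 2.9 rather than 2.1 points would hardly change how haloperidol use is read. That limits the consequence. It does not make the wording of 7.1 correct, and an analysis plan would not normally be expected to repair a sampling assumption stated in the sample-size section.

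**Conclusion.** The point holds for section 7.1. The section states a design that contradicts sections 3.1, 5.1.1 and 7.2, and its precision figure is the independence result, with no allowance for clustering. An ICC of zero is hard to defend given the protocol's own ICU-level predictors and site-specific delirium scores. With 20 patients per ICU and equal sizes, the half-width grows from 2.1 points to 2.9 at an assumed ICC of 0.05 and to 3.5 at 0.10. Unequal ICU sizes widen it further.

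For section 7.3 the conclusion is only conditional: if the intervals and the risk-factor model were fitted without regard to ICU, the intervals would be too narrow and tests of ICU-level covariates would exceed their nominal 5%.

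**What to change.** In 7.1, replace the case-control and simple-random-sampling wording with the actual design: a cohort of all eligible acute admissions, clustered in about 50 ICUs. Restate the expected interval with a design effect over a stated ICC range, for example about 10.6%-15.4% at 0.02, 10.1%-15.9% at 0.05 and 9.5%-16.5% at 0.10, and say that the ICC is assumed.

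Alongside this, add a sentence to 7.3, or confirm in the analysis plan, that the confidence intervals and the risk-factor model account for ICU. Any standard method will do: a random intercept, generalised estimating equations or cluster-robust errors.

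The cost is a few sentences and, if not already planned, an option in the analysis code. No additional patients are needed. The price is that the stated precision becomes less favourable.

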4.3.2 Secondary

1. Number of ICU patients with delirium intervened with other antipsychotics than haloperidol
(Definition: Patients receiving one or more doses of 2nd generation anti-psychotics² including olanzapin (N05AH03), rivastigmin (N06DA03), risperidon (N05AX08) and quetiapine (N05AH04),

¹ Denmark, Norway, Sweden, Finland, Netherland, Switzerland, Germany, United Kingdom, Belgium, Spain, Italy, Canada, Brazil and France

AND described as delirious (see definition in secondary outcome 2. Number of patient with delirium)

2. Number of patients with delirium

(Definitions: ICU documented CAM-ICU positive or ICDSC ≥ 4 points (0-8 points) or DOS >3 points (0-13/day points), ICD-10 code (DF05, DF050, DF05), or agitated and/or non-cooperative and/or eyes open wide with no contact (Glasgow Coma Score (GCS) > 7) or restrained to the bed).

3. Mortality at 90 days

(Definition: Death within 90 days of ICU admission)

4. Days alive in ICU without coma and/or delirium

(Definition Coma: Number of calendar days the patient is alive without coma in the period from ICU admission to discharge. Coma defined as RASS (Richmond Agitation Sedation Score) score -3 to -5, Ramsey sedation score 4 to 6, MASS (Motor Activity assessment Scale) 1 to 0 and GCS < 8 . Delirium Definition: Number of calendar days the patient is alive without delirium in the period from ICU admission to discharge. Delirium defined as above in secondary outcome 2. All assessments in a 24 hour period need to be negative for a patient to be assessed delirium-free).

5. Days alive without mechanical ventilation and days alive out of hospital (ICU) in a 90-day period

(Definition: Patient treated with mechanical ventilation either endotracheal intubated or tracheostomy, on controlled or spontaneous mode or patient treated with continuous non-invasive ventilation (NIV) for more than 1 hour. Number of days without a ventilator is registered every 24 hours; every new day at 6 AM is registered as one day. If a patient is re-intubated/or started NIV within 24 hours it will be registered as a full day of mechanical ventilation.

Definition: Number of days alive after discharge from the hospital (ICU), the day of discharge do not count, but from the next day at 6 AM).

6. Rate of cognitive impairment at 6 months after ICU discharge (only in Denmark)

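### The 95% confidence interval given for 90-day mortality (23%–38% from 1000 patients) is wrong; 1000 patients at 30% give about 27%–33%

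*Protocol*

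**What the plan says.** Section 7.1 of the protocol makes two precision statements, both for 1000 patients.

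- The setting is described as "In a case control study with a simple random sampling". No design effect or allowance for clustering is given.
- For haloperidol use, the expected rate is 13%, and at least 1000 patients are "required to yield a 95% confidence interval of a rate of haloperidol use of 11%-15" per cent.
- For death, the statement is: "With expected mortality rate of 30% 1000 patients will yield a 95% confidence interval of 23% - 38% for 90-day mortality".

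Section 4.1 gives the same total: "We expect to include 1000 acutely ill patients admitted to the participating ICUs". Section 4.3.2 defines the mortality outcome as "Death within 90 days of ICU admission", with no restriction to a subgroup. Section 7.2 defines the analysis population as all patients acutely admitted to a study ICU during the 14-day period. No section gives a smaller denominator for mortality.

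**The concern.** An interval of 23%–38% around 30% is too wide for 1000 patients. It is also much wider than the 11%–15% that the same paragraph derives from the same number. A rate of 30% has a larger variance than a rate of 13%, but not by enough to turn a half-width of 2 points into one of 7.5.

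This is the protocol's only statement of precision for 90-day mortality, which is a listed secondary outcome and the dependent variable of the planned model of haloperidol and death in section 7.3. If the interval is meant for the whole cohort, it understates what the study will deliver. If it was worked out for a smaller group, the denominator is misnamed, and the reader is not told which group has a precision of about ±7.5 points.

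**Working it through.** **Inputs, all from section 7.1:** n = 1000; expected mortality p = 0.30; 95% confidence, taken as two-sided (z = 1.96); simple random sampling; haloperidol rate 0.13.

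**1. The haloperidol interval, as a check on the method.**
Half-width = 1.96 × √(0.13 × 0.87 / 1000) = 0.0208.
Interval: 10.9%–15.1% (Wald); Wilson 11.1%–15.2%. Both round to the printed 11%–15%, so this figure reproduces under simple random sampling with n = 1000.

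**2. The mortality interval from the stated inputs.**
Half-width = 1.96 × √(0.30 × 0.70 / 1000) = 0.0284.

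| Method, 300/1000 | 95% interval |
|---|---|
| Wald | 27.2%–32.8% |
| Wald, continuity-corrected | 27.1%–32.9% |
| Wilson | 27.2%–32.9% |
| Clopper-Pearson | 27.2%–33.0% |
| Agresti-Coull | 27.2%–32.9% |
| Jeffreys | 27.2%–32.9% |

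All round to 27%–33%. The printed 23%–38% does not reproduce. A higher confidence level does not explain it either: a 99.9% Wald interval is 25.2%–34.8%, still narrower than the one printed.

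**3. Size of the discrepancy.**
Printed half-width: (38 − 23)/2 = 7.5 points, against 2.84. Ratio 7.5/2.84 ≈ 2.6.
Sample size with that half-width at 30%: 1.96² × 0.21 / 0.075² ≈ 143.

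**4. Could it be an unstated design effect?**
The implied design effect is 1000/143.4 ≈ 7.0. Applied to the haloperidol rate, it gives a half-width of 1.96 × √(7.0 × 0.13 × 0.87 / 1000) ≈ 0.055, so about 7.5%–18.5%. That contradicts the 11%–15% in the same paragraph.

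**5. Could it belong to a smaller group?**
The companion calculation implies 0.13 × 1000 = 130 haloperidol-treated patients. If the 30% mortality is assumed to apply to them, that is 39/130.

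- Wilson centre: (0.30 + 1.96²/260) / (1 + 1.96²/130) = 0.306.
- Wilson half-width: 1.96 × √(0.21/130 + 1.96²/(4 × 130²)) / (1 + 1.96²/130) = 0.078.
- Wilson interval: 22.8%–38.4%, which rounds to 23%–38%.

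The match depends on the method. At n = 130, Wald gives 22.1%–37.9% and Clopper-Pearson gives 22.3%–38.7%, and neither rounds to 23%–38%. Other sizes also fit at 30%: 126–160 with Wilson, 127–160 with Agresti-Coull, 126–156 with Jeffreys and 139–169 with Clopper-Pearson. So the printed interval corresponds to somewhere between about 126 and 169 patients, and 130 is one candidate among these.

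**The case against.** The arithmetic is not in dispute; the objection concerns its consequence. The 1000 patients are required for the haloperidol interval, which belongs to the primary outcome and is correct. The mortality sentence only reports what that number would yield. Correcting it changes neither the sample size, nor eligibility, nor data collection, nor any analysis in section 7.3. If the whole cohort is meant, the error is conservative and the study will do better than promised. If a group of about 130 was meant, the interval is about right and only the denominator is wrong. The explanation by 130 haloperidol-treated patients is also conjecture: the protocol never names the Wilson method, and it gives neither a mortality interval nor an expected mortality for that group.

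These points stand, and they limit the consequence. They do not make the sentence correct. It gives a figure for a listed outcome that its own inputs contradict, and a reader cannot tell whether the interval or the denominator is the mistake.

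**Conclusion.** Wrong as written. Under the protocol's own assumptions (1000 patients, 30% mortality, 95% two-sided confidence, simple random sampling), the interval is about 27%–33%. The printed 23%–38% is about 2.6 times too wide and has the precision of roughly 143 patients. The conclusion does not depend on the choice of interval method, and the correct haloperidol interval beside it rules out a common design effect. The error does not affect the planned sample size. Whether the authors miscalculated or attached a subgroup's interval to the whole cohort cannot be settled from the protocol.

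**What to change.** Replace the mortality sentence in section 7.1 with, for example:

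*With an expected 90-day mortality of 30%, 1000 patients yield a 95% confidence interval of about 27%–33%, assuming simple random sampling and before any allowance for clustering by ICU.*

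If 23%–38% was intended for haloperidol-treated patients, keep it in a separate sentence that names the group, its expected size (about 130, from 13% of 1000), the 30% mortality assumed within it, and the interval method. The authors should state which was meant.

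The cost is one or two sentences in section 7.1. The sample size, data collection and analyses stay as they are.

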7.2 Population to be analysed

All patients who are acutely admitted to one of the study ICUs at any point of the 14-day study period (the 1st day at 00:01 to the last day at 23:59).

7.3 Statistical plan

The number of patients receiving haloperidol (totally and regularly, as needed and mixed dosing) will be presented as frequencies (% with 95% confidence intervals). Numeric data will be given as medians (interquartile range [IQR]). We will compare differences in baseline characteristics using non-parametric tests between patients who receive haloperidol and patients who do not receive haloperidol. To assess risk factors for the use of haloperidol, we will do multivariate analyses including patient characteristics (age, dialysis, shock and mechanical ventilation and delirium in the first 24 h of admission) and ICU characteristic (university hospital, guidelines for identifying and/or treating delirium and average staff-patient ratio). To assess if haloperidol is an independent predictor of 90-day mortality, we will do multivariate analysis including patient characteristics (age, dialysis, shock and mechanical ventilation and delirium in the first 24 h of admission) and time. We will do exploratory analyses on the interaction between delirium and use of haloperidol and the patient-relevant outcomes measure (mortality, days alive without mechanical ventilation and days alive and out for hospital). All statistical tests will be 2-tailed and $p < .05$ considered statistically significant.

8. Data Handling

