2.2 Study Objectives

2.2.1 Aim

To describe and explore current use of haloperidol and other pharmacological interventions for delirium in critically ill patients admitted to ICUs in selected countries¹.

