4.3 Primary and secondary outcome measures

4.3.1 Primary

Number of ICU patients with delirium intervened with haloperidol (N05AD01)

(Definition: Patients receiving one or more doses of haloperidol and are described as delirious. Delirium defined as below in secondary outcome 2).

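### The haloperidol risk-factor model is not limited to delirious patients and adjusts only for first-24-h delirium, so it can mistake causes of later delirium for drivers of prescribing

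*Protocol*

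**What the plan says.** Four parts of the protocol bear on this point.

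- **Population.** Section 7.2 defines one analysis population: "All patients who are acutely admitted to one of the study ICUs at any point of the 14-day study period". It is not limited to patients with delirium.
- **Risk-factor model.** Section 7.3 says: "To assess risk factors for the use of haloperidol, we will do multivariate analyses including patient characteristics". The patient covariates, running into the ICU covariates, are "age, dialysis, shock and mechanical ventilation and delirium in the first 24 h of admission) and ICU characteristic". The ICU covariates are university hospital, "guidelines for identifying and/or treating delirium and average staff-patient ratio". Early delirium is the only delirium term.
- **Baseline comparison.** The comparison in the same section is "between patients who receive haloperidol and patients who do not receive haloperidol", again without restriction.
- **Purpose.** The aim in 2.2.1 is "To describe and explore current use of haloperidol and other pharmacological interventions for delirium", and the primary outcome in 4.3.1 is "Number of ICU patients with delirium intervened with haloperidol".

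Section 6.1 collects delirium status daily through the ICU stay. Item 19a records haloperidol with a prophylaxis flag. Section 2.1 lists age among the risk factors for delirium and gives an incidence range of 16% to 89%.

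**The concern.** Receiving haloperidol for delirium takes two steps: the patient becomes delirious (and is recognised as such), and the clinician then chooses haloperidol. A model in all admissions mixes the two steps. Adjusting for first-24-h delirium blocks the first step only for delirium already present on day 1.

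Age is in the model, and section 2.1 names it as a cause of delirium. Shock, dialysis and ventilation may act in the same way, since 2.1 also lists acute severe illness. If such a factor raises the risk of delirium on day 3 and has no bearing on how delirious patients are treated, the model still gives it an odds ratio above 1. If a factor raises delirium but lowers prescribing, the two effects can offset each other and a real practice difference goes unseen.

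Section 2.1 wants knowledge of current haloperidol use in order to design later trials. Determinants of delirium and determinants of treatment choice would inform such designs differently.

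**Working it through.** **1. The protocol's own figure.** Section 7.1 gives 11%-15% for a 13% rate with 1000 patients. 0.13 ± 1.96 × √(0.13 × 0.87 / 1000) = 0.13 ± 0.021, that is 10.9% to 15.1%. The figure reproduces with all 1000 admissions as denominator, which supports reading 7.3 as an all-patient analysis. The protocol gives no figure for the risk-factor model itself.

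**2. The mechanism by hand.** These inputs are assumptions, not from the documents: a factor X present in 50% of patients; delirium in 30% without X; odds ratio 2 of X on delirium; half of delirium in the first 24 h; haloperidol in 40% of delirious and 1% of non-delirious patients, whatever X is.

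- Delirium odds without X: 0.30/0.70 = 0.429. With X: 0.857, so the risk is 0.857/1.857 = 46.2%.
- Patients without early delirium, X absent: 15% late delirium and 70% none. Haloperidol = (0.15 × 0.40 + 0.70 × 0.01)/0.85 = 7.9%.
- Patients without early delirium, X present: 23.1% late and 53.8% none. Haloperidol = (0.231 × 0.40 + 0.538 × 0.01)/0.769 = 12.7%.
- Odds ratio in that stratum: (0.127/0.873)/(0.0788/0.9212) = 1.70. In the early-delirium stratum it is 1, since 40% are treated either way.
- The planned type of model pools the strata and gives 1.39 (expected 95% CI 0.97-2.01 at 1000 patients). Among all delirious patients the odds ratio is 1.00.
- If all delirium is early, the stratum without early delirium contains no delirium. Its odds ratio is then 1 and the bias is gone.

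**3. Range of the bias.** The calculation was repeated over delirium of 20%, 30% and 40% without X; 25%, 50% and 75% of delirium early; and odds ratios of 1.5, 2 and 3 on delirium (27 settings). The all-patient model gives odds ratios from 1.12 to 2.01, always above 1. The expected CI excludes 1 in 9 of the 27. The delirious-only model gives 1.00 throughout.

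**4. False-positive rate.** Simulation with 1000 patients, 13% on haloperidol (7.1), all users delirious, X in 50%, odds ratio 2 of X on delirium, no effect of X on prescribing, no clustering by ICU, and adjustment for age and early delirium. Each cell shows 1000 runs, then a separate set of 600.

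| Delirium prevalence | One third early | 60% early |
|---|---|---|
| 20% | 79% / 74% | 47% / 46% |
| 30% | 63% / 65% | 36% / 30% |
| 50% | 41% / 39% | 24% / 26% |

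Restricted to delirious patients, the same model rejects in 4%-6%.

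**5. Cancellation.** X doubles the odds of delirium and halves the odds of haloperidol given delirium. At 30% prevalence, the all-patient model detects X in 4.5% of studies (odds ratio 0.98), against 82% (0.49) among delirious patients. At 20% and 50% prevalence the rates are 22% against 57%, and 29% against 92%. The masking is thus near complete at 30% and partial elsewhere.

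**6. Where restriction itself misleads.** Assume 15% hyperactive delirium, always recorded, and 15% hypoactive delirium, recorded in 80% with a detection guideline and 40% without. Haloperidol is given to 60% and 10% of these groups, and the guideline does not affect prescribing.

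- With the guideline: (0.15 × 0.60 + 0.12 × 0.10)/0.27 = 37.8%.
- Without: (0.15 × 0.60 + 0.06 × 0.10)/0.21 = 45.7%.
- Delirious-only odds ratio: (0.378/0.622)/(0.457/0.543) = 0.72, with a true value of 1.

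With 0.5% use in non-delirious patients added, the all-patient model gives 0.85 to 0.93 when 33% to 60% of recorded delirium is early.

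**The case against.** The strongest reply is that 7.3 asks who receives haloperidol, and an all-admissions model with baseline covariates answers that validly. The research question in 2.2.2 is which agents are used and how they are given; nowhere does the protocol announce a causal reading conditional on delirium. This stands: a reader might infer that the planned model is invalid and should be replaced, and the documents do not support that.

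A reader might also infer that 4.3.1 fixes delirious patients as the denominator. It does not. It defines a count, and the only denominator behind a stated figure is all 1000 patients.

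Third, 7.3 does not itself name the model's population, and a statistical analysis plan that is not at hand could restrict it. This is true, but 7.2 and 7.3 together do fix a population and a covariate list, and as written these do not separate delirium from its treatment.

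Fourth, the sizes rest on assumptions. The simulations leave out the other planned covariates and ICU clustering. Clustering matters most for guidelines, which vary only between an estimated 50 ICUs. This stands, and it makes the percentages illustrative.

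Fifth, restriction conditions on recorded delirium, which depends on local detection: under 6.1, sites register only the tool they use. Step 6 shows that for a detection guideline the restricted estimate can lie further from the truth. This also stands, and it is why the restricted model should be added and not substituted.

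**Conclusion.** The point holds in a limited form. As written, the model can present causes of delirium after day 1 as risk factors for haloperidol use, and it can hide a prescribing difference that runs against an effect on delirium. The direction of the bias needs only that haloperidol is commoner in delirious patients and that some delirium starts after 24 h.

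Under the stated assumptions (odds ratio 2 on delirium, prevalence 20% to 50%, one third to 60% early, no clustering), the false-positive rate is roughly 25% to 75%. With smaller effects or mostly early delirium, the bias is often too small to reach significance.

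A reader might infer that the analysis would return mainly delirium risk factors. Neither the documents nor the calculations show that: the expected interval excluded 1 in only 9 of 27 settings. The flaw lies in what the model may be taken to show about treatment of delirium, and it affects a secondary analysis. An inexpensive addition deals with it.

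**What to change.** In section 7.3:

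1. Keep the all-patient model, labelled as predictors of receiving haloperidol among all acute admissions, including through the occurrence of delirium.
2. Add the same model, and the haloperidol versus no-haloperidol baseline comparison, in patients who meet the secondary outcome 2 definition at any time in the ICU. Draw conclusions about prescribing for delirium from this model.
3. Report haloperidol given without recorded delirium separately, using the prophylaxis field in item 19a.
4. State that the coefficient for guidelines for identifying delirium is affected by detection differences in both models and is not a pure prescribing effect.

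The cost is wording, since the daily data are already collected. The statistical price is a smaller sample: about 160 to 890 of 1000 patients over the incidence range in 2.1. At low prevalence, untreated delirious patients become the limiting class. With 130 treated, 20% delirium leaves 200 − 130 = 70 untreated, and 16% leaves 160 − 130 = 30, for about eight covariates. The covariate list may need trimming, and the rule for doing so should be set in advance.
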